- IPSS after 12 months in both groups (Mw ± SD) = 4 ± 4
- n (group BipolEP) / n (group TURP) = 1 / 1
- Parametric test

The result of the sample size estimation is a requirement of 31 cases per group. Assuming a drop-out rate of 20% and considering the possible need for a non-parametric test a total of 84 inclusions (n=42 / group) are chosen as the sample size of the study.

Analysis Populations:

Intent-to-treat (ITT) population: All subjects at whom the group-specific treatment (TURP, BipoIEP) at least has started will be included in the ITT population. All variables will be analysed.

Per-protocol (PP) population: All subjects without occurrence of any drop-out situation (all valid cases) will be included in the PP population. All variables will be analysed. The PP analysis is paramount.

Handling of Implausible Values and of Missing Values:

Implausible values have to be identified during the data management process in agreement with the clinical investigator. They will be converted into missing values.

Missing Values will be replaced only in the ITT population and only for the two primary endpoints. The replacements will be made according to the worst-case principle (use of the worst assessed value in the study).

Post-hoc Analyses:

Analyses of subgroups and other post-hoc analyses can be performed for cause. However, all statistical results will be only descriptive.

Interim Analyses:

A priori no interim analysis is intended.

Presentation of the Results (Descriptive Analysis, Graphs etc.):

Categorical variables will be presented using counts and percentages. Variables measured on ordinal scales will be presented using counts and percentages (where appropriate) or minimum, 25%-percentile, median, 75%-percentile and maximum and number of patients (where appropriate). Continuous variables will be presented using minimum, 25%-percentile, arithmetic mean, median, 75%-percentile, maximum, standard deviation and number of patients.

All results will be presented in the form of tables, selected results additionally in the form of graphs (bar charts, boxplots).

Allcation

For the allocation of treatment to subjects the minimization method will be used (manual see accompanying documents).

	Strata:
	prostate 60 to 80 ml / more than 80 ml
	catheterized / non-catheterized
	The minimization procedure will be applied centrally (by the coordinating centre).

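### In the supporting ITT analysis, missing 12-month IPSS in either arm is set to the trial's worst score, so the result shifts against whichever arm loses more patients and is hard to interpret beside PP when losses are unequal

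*Combined protocol and SAP*

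**What the plan says.** All references are to the statistical analysis part of the combined protocol and SAP unless stated.

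- **Analysis Populations.** ITT takes in everyone whose allocated treatment "at least has started will be included in the ITT population". For PP: "All subjects without occurrence of any drop-out situation (all valid cases) will be included in the PP population". On priority: "The PP analysis is paramount".
- **Handling of Implausible Values and of Missing Values.** Of implausible values it says: "They will be converted into missing values". On scope: "Missing Values will be replaced only in the ITT population and only for the two primary endpoints". On method: "The replacements will be made according to the worst-case principle (use of the worst assessed value in the study"). No arm is singled out, so both receive the same value.
- **Sample Size Justification.** The step from 31 to 42 per group is explained by: "Assuming a drop-out rate of 20% and considering the possible need for a non-parametric test".
- **Statistical Methods, Primary Endpoint (1).** A Lilliefors normality check at 10% decides between a parametric and a non-parametric one-sided test against a margin of 3, at one-sided 5%. A log transform is allowed.

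No other missing-data method or sensitivity analysis is given, and nothing says how the ITT result is to be read beside PP.

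**The concern.** In a non-inferiority comparison, a pessimistic assumption has to count against the experimental arm. This rule counts against both arms, in proportion to the number of men each has lost. Extra losses on TURP make TURP look worse and help BipolEP pass. Extra losses on BipolEP do the reverse, even when the treatments are equal. Values judged implausible go the same way: they are first set to missing and then, in ITT, become the worst score.

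PP leaves out every drop-out. ITT is therefore the only planned analysis that keeps treated men who drop out, and the only planned check on whether selective loss has shaped the PP result. What is at stake is whether that check says anything about the treatments. The point concerns 12-month IPSS only.

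**Working it through.** **Inputs from the plan.** Margin 3; one-sided 5%; power 90%; 12-month IPSS 4 ± 4 in both groups; 42 enrolled per group; drop-out 20% (0.20 × 42 = 8.4, so about 8 per group).

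**1. The plan's own figure.** n = 2 × [(1.645 + 1.282) × 4 / 3]² = 30.4, so 31 per group, as stated. Drop-out alone gives 31 / 0.8 = 38.75, so 39. With an assumed non-parametric efficiency of 0.955 (not in the plan), 31 / 0.955 gives 33, and 33 / 0.8 = 41.25 gives 42. The sample size is not in dispute.

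**2. What the rule does to the difference.** Let m_B and m_T be the numbers missing on BipolEP and TURP, W the worst score, and d the true difference, with a TURP mean of 4. The expected ITT difference is

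d × (1 − m_B/42) + (m_B − m_T) × (W − 4)/42.

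- Equal arms (d = 0): each extra missing patient moves the difference by (W − 4)/42. In simulation W averages 13.5 for normal scores and up to 21.1 for skewed ones. This gives 9.5/42 = 0.23 to 17.1/42 = 0.41 points, in favour of BipolEP if the patient was on TURP and against it if on BipolEP.
- d = 3, 8/8 missing: 3 × 34/42 = 2.43.
- d = 3, 6/10 missing (BipolEP/TURP), W = 15.64: 3 × 36/42 − 4 × 11.64/42 = 2.57 − 1.11 = 1.46.
- d = 3, 10/6 missing, W = 15.51: 3 × 32/42 + 4 × 11.51/42 = 2.29 + 1.10 = 3.38.

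So the same true difference, sitting on the margin, shows up as 1.46 or 3.38 depending only on which arm lost four more men.

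**3. How often the arms differ.** With 20% missing at random in each arm (binomial, n = 42), the counts differ by 2 or more with probability 0.68, and by 4 or more with probability 0.34.

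**4. Effect on the test.** Settings: 42 per arm; mean 4, SD 4, with normal, gamma or negative binomial scores; missing at random; W the worst observed 12-month score in either arm; test chosen by the plan's normality check, with no log transform. The plan names no non-parametric test for this endpoint, so Mann-Whitney is assumed, as for endpoint 2. PP is taken as observed cases. There were 1,500 simulated trials per cell, so the standard error is √(0.05 × 0.95/1500) = 0.006 near 0.05 and √(0.22 × 0.78/1500) = 0.011 near 0.22.

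| Missing (BipolEP/TURP) | ITT pass rate at true difference 3 (nominal 0.05) |
|---|---|
| 10% at random | 0.06-0.08 |
| 20% at random | 0.09-0.11 |
| 3/5 | 0.08-0.12 |
| 6/10 | 0.21-0.23 |
| 10/6 | below 0.01 |
| Observed cases | about 0.04-0.06 |

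At 5% missing, running each test separately (20,000 trials), the ITT rate is 0.050-0.065.

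Power with equal arms:

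- 8/8: almost unchanged.
- 9/7: from 0.93 to 0.79 for normal scores, and from 0.98-0.99 to 0.91-0.95 for skewed scores.
- 20% at random: PP passes but ITT fails in about 0.06-0.11 of trials.

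**5. What is not affected.** PP uses no replaced values. A rule that PP and ITT must both pass cannot succeed more often than PP alone. In the 20,000-trial runs with missing data it did so in at most 0.052 of trials at a true difference of 3.

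**The case against.** The strongest reply is that PP leads and contains no replaced values, so the trial's main decision is untouched. That stands, and it limits the point to a supporting analysis.

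Second, 20% is a drop-out allowance for sample size. ITT counts only men whose treatment started, and a man excluded from PP may still have a 12-month score. ITT missingness may well be lower, and at 5% the distortion is small. This also stands.

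Third, a reader might infer that power collapses when scores are skewed, because imputed extremes inflate the variance in a t-test. The plan does not lead there. With skewed scores its normality check rejects in essentially all ITT datasets, so the non-parametric test is used and the loss is modest. Only a log transform that restored normality could change this, and that was not simulated.

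Fourth, one could read the worst score as including baseline, where entry requires IPSS above 15, which would enlarge every shift. But the replacement is for a primary endpoint defined as IPSS after 12 months, so the working uses 12-month scores only.

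Finally, imputation is not shown to beat observed cases when loss is unrelated to outcome. A check with one 4-month score, an assumed correlation of 0.5 and 20 imputations gave type I error 0.045-0.054 and power 0.91-0.93, much like observed cases. That is fair. The gain is that treated drop-outs are kept, their earlier scores are used, and the result no longer follows the loss counts. A larger imputation model was not tested. A pooled mean difference in ITT beside a rank test in PP would also create a new mismatch, which the fix has to avoid.

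**Conclusion.** The point holds for the supporting ITT analysis of 12-month IPSS and should be fixed. The rule is called worst-case, but it can help BipolEP as easily as hurt it. At a true difference equal to the margin it roughly doubles the ITT pass rate under 20% random loss and about quadruples it at 6/10, while at 10/6 the pass rate is close to zero.

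Two stronger readings are not supported. One is that the trial's non-inferiority claim carries an inflated error: neither the PP test nor a requirement that both analyses pass does. The other is that ITT can never be set against PP: with few or equal losses they agree closely. What fails is attribution under unequal loss, when neither agreement nor disagreement can be credited to the treatments.

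The direction of the effect is arithmetic. Its size rests on the assumed missing rate, missingness at random, the three score distributions, Mann-Whitney as the non-parametric test, and no log transform. The number of implausible values is unknown and was not quantified.

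**What to change.** 1. In ITT, replace the worst-value rule for 12-month IPSS with multiple imputation by arm from baseline, 1-month and 4-month IPSS. Keep the model small, since only about 34 to 42 men per arm will inform it. A mixed model on the same visits is an acceptable alternative.
2. Compare the upper one-sided 95% limit of the mean difference with 3. Report the same mean difference and limit in PP, so that the two analyses differ only in population and missing-data handling. State in a sentence how a disagreement will be read.
3. Add a tipping-point analysis that worsens only the BipolEP imputations until non-inferiority is lost, and report how much worsening that takes. This supplies the pessimism in the direction that matters.
4. Treat implausible values that cannot be resolved as ordinary missing values, not as the worst score. Report missing counts and reasons by arm.

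The cost is SAP wording and modest extra analysis. The planned follow-up already has IPSS at 1 and 4 months, so no new visits or data are needed. The price is reliance on a missing-at-random assumption, which step 3 tests. The prostate-volume strata, which start at 60 ml although men from 40 ml are eligible, are a separate issue, and this fix does not depend on them.

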	The study is designed as a comparison of two kinds of treatment: Group BipolEP: Bipolar transurethral enucleation of the prostate Group TURP: Bipolar transurethral resection of the prostate
	Two primary endpoints are chosen: (1): IPSS after 12 month [-] (2): Tissue resection [g/min]
	The use of a gate keeping approach makes it unnecessary to adjust the type I error. Primary endpoint (1) will be investigated by a non-inferiority approach (type I error = 5% one-sided), primary endpoint (2) by a superiority approach (type I error = 2.5% one-sided).
	Hypotheses:
	(1): H-0 ₁ : Compared to group TURP, IPSS after 12months in group BipoIEP is higher (non-inferiority range = 3) H-1 ₁ : Compared to group TURP, IPSS after 12months in group BipoIEP is not higher (non-inferiority range = 3)
	(2): H-0 ₂ : Compared to group TURP, tissue resection in group BipolEP is not increased H-1 ₂ : Compared to group TURP, tissue resection in group BipolEP is increased
Statistical	Statistical Methods:
analysis	Group Comparisons:
	Primary Endpoint (1): Data (if appropriate, in logarithmised version) will be checked for normal distribution (Kolmogorov-Smirnov with Lilliefors significance correction, type I error = 10%). Hypotheses (H-0 ₁ , H-1 ₁) will be investigated either by a parametric or by a non-parametric one-sided test of equivalence (equivalence range one-sided = 3; type I error = 5% one-sided).
	Primary Endpoint (2): Data (if appropriate, in logarithmised version) will be checked for normal distribution (Kolmogorov-Smirnov with Lilliefors significance correction, type I error = 10%). Hypotheses will be investigated either by the t-test for independent samples or by the Mann-Whitney U-test (type I error = 2.5% one-sided). Hypotheses (H-0 ₂ , H-1 ₂) will be tested only if H-0 ₁ hypothesis is rejected.
	Further Variables: All other variables will be analysed by usual parametric and non-parametric tests for univariate comparisons of independent samples.
	Two-sided 95% confidence intervals: For selected variables, two-sided 95% confidence intervals will be calculated.
	Type I error adjustment: No adjustment for the type I error will be made. Therefore – apart from hypotheses testing – the results of inferential statistics will be descriptive only.
	Sample Size Justification:

The following scenario was used for the sample size estimation concerning primary endpoint (1):

- Non-inferiority range = 3
- Type I error = 5% one-sided
- Type II error = 10%

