	According to the allocation approach and the multicentre nature of the study minor deviations in defined group BipolEP / group TURP ratio of 1 / 1 cannot be excluded.
	First patient in to last patient out (months): 36
Trial duration	Duration of the entire trial (months): 36
	Recruitment period (months): 12
Participating	N = 2
centres	

Intervention scheme/ Trial flow

1. 1. The Medical Problem

Lower urinary tract symptoms (LUTS) caused by prostatic enlargement (benign prostatic hyperplasia, BPH) are a common problem in elderly men. It is well known that the incidence of LUTS is rising with age and there are reported incidence rates of 38 cases per 1000 man-years at the age of 75-79 years [1]. In the EAU guidelines LUTS is divided in three different groups, mild, moderate and severe, by using the international prostate symptoms score (IPSS). Surgical intervention is recommended for moderate to severe LUTS. However, transurethral resection of the prostate (TURP) is still representing the gold standard [2]. On the other hand the surgical approach is changing from conventional monopolar TURP to minimally invasive surgical techniques such as holmium laser enucleation (HoLep) or GreenLight lithium borate laser vaporization (PVP) [1] or other minimal invasive techniques. Transurethral enucleation of the prostate (TUEP) has been available as a monopolar current-based enucleation—resection since it was first described by Hiraoka in 1983 [3]. Although it was the blueprint for all other transurethral enucleations to come, it remained a local phenomenon in Japan [4]. Only when enucleation was in focus again with laser technology and the mechanical tissue morcellator, did it come into focus after publication of a paper on holmium laser enucleation of the prostate (HoLEP) in 1998 by Fraundorfer and Gilling [5]. HoLEP is regarded as a standard approach for the treatment of large prostate glands, and the great evidence base is mentioned in support of that. However, only in 2006 there was the first randomized controlled trial on HoLEP versus bipolar enucleation (plasmakinetic enucleation of the prostate, PKEP) published by the same group [6].

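### Centre is neither a listed minimisation factor nor a term in either confirmatory analysis, so chance imbalance of centre between arms is neither limited nor adjusted for in this two-centre surgical trial

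*Combined protocol and SAP*

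**What the plan says.** The allocation section at the end of the protocol's statistical analysis text states: "For the allocation of treatment to subjects the minimization method will be used (manual see accompanying documents". The manual is a separate document and was not available for this review. The strata listed beneath are "prostate 60 to 80 ml / more than 80 ml" and "catheterized / non-catheterized"; no third factor appears. On where allocation is run: "The minimization procedure will be applied centrally (by the coordinating centre". The participating-centres row gives two centres.

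The only remark on the multicentre design concerns the overall ratio: "multicentre nature of the study minor deviations in defined group BipolEP / group TURP ratio of 1 / 1 cannot be excluded". It does not address the split between arms within a centre.

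The confirmatory endpoints, under Concept, are "1): IPSS after 12 month [-] (2): Tissue resection [g/min". Under Statistical Methods, endpoint 1 "will be investigated either by a parametric or by a non-parametric one-sided test of equivalence" (margin 3, one-sided 5%). Endpoint 2 is compared by a t-test or Mann-Whitney test (one-sided 2.5%), only if endpoint 1 succeeds. Neither analysis contains a centre term. The documents do not say how many surgeons operate, what experience they have, or who performs which procedure.

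**The concern.** Centre may well be prognostic in a surgical trial. Endpoint 2 is a rate of tissue removal, so it directly reflects operating speed, and the experimental arm uses a recently introduced electrode. The sponsor chose minimisation in order to balance prognostic factors and runs it centrally, so the patient's centre can be known at each allocation, yet centre is left out. The planned tests do not compensate.

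Two things are at stake. A centre difference left in the residual variance costs power. And in the one allocation that is actually realised, any chance difference in centre mix moves the estimate by the centre difference multiplied by the imbalance, with nothing in the analysis to remove it.

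**Working it through.** **1. The plan's own figure.** Inputs from Sample Size Justification: margin 3, SD 4, true difference 0, one-sided 5%, power 90%. n = 2 × 4² × (1.645 + 1.282)² / 3² = 30.45, so 31 per group. This agrees with the plan. Exact power with the t distribution is 89.9% at 31 per group. Dropout: 31 / 0.8 ≈ 39; 42 per group leaves room for the rank test. None of this changes below.

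**2. Size of the chance imbalance.** The documents give no figure, so these are assumptions: centre shares 30–50%, 50% of glands over 80 ml, 25% catheterised, minimisation either deterministic or following the preferred arm with probability 0.8.

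Rough check by hand: if centre is ignored, the difference in centre share between arms of 42 has SD √(2p(1−p)/42), which is √(0.5/42) = 10.9 points at p = 0.5 and √(0.42/42) = 10.0 points at p = 0.3.

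Simulated trials of 84 men:

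| | As planned | Centre as third factor |
|---|---|---|
| SD of imbalance (points) | 10–11 | 2–3.5 |
| 10 points or more, either direction | 28–35% | about 1% or less |
| 20 points or more | 4–7% | about 0% |

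The benefit is smaller among evaluable men. With random loss to 66 men, 10 points or more occurs in about 38–41% of trials as planned and 6–11% with the factor; my repeat gave 38–42% and 8–13%.

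**3. Effect on endpoint 1 across all allocations.** Simulation with 62 evaluable men, equal centres, deterministic minimisation and within-centre SD 4:

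| Assumed centre difference (IPSS points) | 0 | 2 | 4 |
|---|---|---|---|
| Type I error, as planned | 5.0% | 4.8% | 4.9% |
| Power, as planned | 89.8% | 88.6% | 83.9% |
| Type I error, factor added, no centre term | 4.9% | 4.6% | 3.3% |
| Power, factor added, no centre term | 90.7% | 88.2% | 85.9% |

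With a centre term, type I error is 4.8–5.2% and power 89–91%, whether or not centre is a minimisation factor.

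The power loss can be checked by hand. A 4-point centre difference gives a total SD of √(16 + 0.25 × 4²) = 4.47. Then SE = 4.47 × √(2/31) = 1.136, and Φ(3/1.136 − 1.645) = 84.0%. At 2 points the SD is 4.12 and power is 88.9%.

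This takes the plan's SD of 4 as the within-centre SD, which the documents do not say. If 4 is the total SD, planned power stays at about 90% and the centre term adds to it: at 2 points, within-centre SD = √(16 − 1) = 3.87 and power is Φ(3/(3.87 × √(2/31)) − 1.645) = 92%.

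**4. Error conditional on an imbalance.** Take a 10-point imbalance favouring BipolEP and a centre difference of d = 0.5–1 SD (assumed). In within-centre SD units the bias is 0.1d, SE = √(2/n), and the planned test uses a pooled SD inflated by r = √(1 + p(1−p)d²). Conditional error = 1 − Φ(z·r − 0.1d/SE).

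- Endpoint 1 (33 per arm, SE 0.246, z 1.645). d = 0.5, p = 0.5: 1.645 × 1.031 − 0.203 = 1.49, so 6.8%. d = 1, p = 0.3: 1.645 × 1.100 − 0.406 = 1.40, so 8.0%.
- Endpoint 2 (42 per arm, SE 0.218, z 1.96). d = 0.5, p = 0.5: 1.96 × 1.031 − 0.229 = 1.79, so 3.7%. d = 1, p = 0.3: 1.96 × 1.100 − 0.458 = 1.70, so 4.5%.

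These apply only to imbalances in BipolEP's favour, about half of those counted in step 2. For the mirror-image imbalance the sign of the bias term changes and the error falls: for endpoint 1, 1.645 × 1.118 + 0.406 = 2.25 gives 1.2% at d = 1, p = 0.5.

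**5. Shift on the IPSS scale.** With equal centres, the 95th percentile of imbalance is 21–26 points. A 2-point centre difference then moves the estimate by 0.4–0.5 points, 14–17% of the margin; a 4-point difference moves it by 0.8–1.0. Endpoint 2 cannot be expressed in g/min because no SD is given.

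**The case against.** The strongest reply is that allocation takes care of this. Minimisation gives no systematic link between arm and centre, the imbalance averages zero, and the unadjusted test keeps its size. That stands. A reader might infer that arm and centre are confounded, or that the trial's false-positive rate is inflated. The documents support neither: the imbalance arises by chance, and the higher error rates in step 4 hold only given an unfavourable allocation.

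It can also be said that the analysis term does most of the work. That stands too: it recovers the power with or without the allocation factor. The factor adds protection mainly if the planned rank tests are used, since they have no place for a covariate, and it limits the imbalance in the realised trial.

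A reader might equate centre with surgeon. That is inference: the documents are silent on surgeons, and balancing centre does not balance surgeons within a centre. A reader might also think that the change is free. It is not, since under deterministic minimisation the share of non-tied, hence predictable, assignments rises from about 72% to 77–79%.

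Finally, the manual may name centre. If so, the protocol's strata list is incomplete and the two should be made to match.

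**Conclusion.** The point holds as a matter of precision and balance, not of bias or overall error control. Centre is absent from both the strata list and the confirmatory tests, although allocation is already central. With no centre difference nothing is lost. With 2 IPSS points between centres the power loss is about one percentage point, and with 4 points about five to six. For endpoint 2 the case is plausible and more direct, because speed depends on the operator, but it cannot be sized in g/min.

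The sizes rest on assumed centre shares, gland and catheter proportions and centre differences, and on reading the plan's SD as within-centre. The omission itself rests on none of these. It is a cheap improvement that the sponsor should make; it does not invalidate the design.

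**What to change.** 1. Include centre (two levels) in the analysis of both confirmatory endpoints: a linear model with arm and centre on the parametric route, and a centre-stratified rank test (van Elteren, with the 3-point margin applied as a shift for endpoint 1) on the non-parametric route.
2. Before allocation starts, add centre as a third minimisation factor, weighted equally with the other two and with a random element, in both the strata list and the manual.

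Make the two changes together. Adding the factor while keeping the unadjusted test makes that test conservative (type I error 3.3% at a 4-point centre difference). If allocation has already begun, the first change alone still recovers most of the power.

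Cost: a few lines in the allocation section, the manual and the analysis text, and no change to 31 evaluable or 42 included per group. The downsides are slightly more predictable allocation, which the random element limits, and slightly looser balance on prostate size and catheter status. The protocol should also state the number of surgeons per centre and who performs which procedure, since this change does not address them.
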